6.3.7 Hy's Law

Cases where a subject shows elevations in liver biochemistry may require further evaluation and occurrences of AST or ALT $\geq 3\times$ ULN together with total bilirubin $\geq 2\times$ ULN may need to be reported as SAEs. Please refer to [Appendix D](#) for further instruction on cases of increases in liver biochemistry and evaluation of Hy's Law.

6.3.8 Disease under Study (DUS)

Symptoms of DUS are those which might be expected to occur as a direct result of active RA. Events, which are unequivocally due to disease under study should not be reported as an AE

during the study unless they meet SAE criteria or lead to discontinuation of the investigational product.

6.4 Reporting of serious adverse events

All SAEs have to be reported, whether or not considered causally related to the investigational product, or to the study procedure(s). All SAEs will be recorded in the CRF.

If any SAE occurs in the course of the study, then Investigators or other site personnel inform the appropriate AstraZeneca representatives within one day i.e., immediately but **no later than 24 hours** of when he or she becomes aware of it.

The designated AstraZeneca representative works with the Investigator to ensure that all the necessary information is provided to the AstraZeneca Patient Safety data entry site **within 1 calendar day** of initial receipt for fatal and life threatening events **and within 5 calendar days** of initial receipt for all other SAEs.

For fatal or life-threatening adverse events where important or relevant information is missing, active follow-up is undertaken immediately. Investigators or other site personnel inform AstraZeneca representatives of any follow-up information on a previously reported SAE within one calendar day i.e., immediately but **no later than 24 hours** of when he or she becomes aware of it.

Once the Investigators or other site personnel indicate an AE is serious in the WBDC system, an automated email alert is sent to the designated AstraZeneca representative.

If the WBDC system is not available, then the Investigator or other study site staff reports a SAE to the appropriate AstraZeneca representative by telephone.

The AstraZeneca representative will advise the Investigator/study site staff how to proceed.

The reference document for definition of expectedness/listedness is the IB for the AstraZeneca drug and the EU Summary of Product Characteristics (SPC) for the active comparator product.

6.5 Overdose

To date there is no experience of overdose and no antidote to AZD9567. In cases of known or suspected overdose, symptomatic treatment and monitoring of vital functions and e.g. blood parameters should be performed according to routine clinical practice based on the judgment of the investigator. In addition, should an overdose occur the following procedures should be followed:

- An overdose with associated AEs is recorded as the AE diagnosis/symptoms on the relevant AE modules in the CRF and on the Overdose CRF module.
- An overdose without associated symptoms is only reported on the Overdose CRF module.

If an overdose on an AstraZeneca study drug occurs in the course of the study, then the Investigator or other site personnel inform appropriate AstraZeneca representatives immediately, or **no later than 24 hours** of when he or she becomes aware of it.

The designated AstraZeneca representative works with the Investigator to ensure that all relevant information is provided to the AstraZeneca Patient Safety data entry site.

For overdoses associated with a SAE, the standard reporting timelines apply, see Section [6.4](#).
For other overdoses, reporting must occur within 30 days.

6.6 Pregnancy

All pregnancies and outcomes of pregnancy should be reported to AstraZeneca except for:

- If the pregnancy is discovered before the study subject has received any study drug

6.6.1 Maternal exposure

If a subject becomes pregnant during the course of the study investigational product should be discontinued immediately.

Pregnancy itself is not regarded as an adverse event unless there is a suspicion that the investigational product under study may have interfered with the effectiveness of a contraceptive medication. Congenital abnormalities/birth defects and spontaneous miscarriages should be reported and handled as SAEs. Elective abortions without complications should not be handled as AEs. The outcome of all pregnancies (spontaneous miscarriage, elective termination, ectopic pregnancy, normal birth or congenital abnormality) should be followed up and documented even if the subject was discontinued from the study.

If any pregnancy occurs in the course of the study, then the Investigator or other site personnel informs the appropriate AstraZeneca representatives within 1 day i.e., immediately but **no later than 24 hours** of when he or she becomes aware of it.

The designated AstraZeneca representative works with the Investigator to ensure that all relevant information is provided to the AstraZeneca Patient Safety data entry site within 1 or 5 calendar days for SAEs (see Section [6.4](#)) and within 30 days for all other pregnancies.

The same timelines apply when outcome information is available.

The PREGREP module in the CRF is used to report the pregnancy and the PREGOUT is used to report the outcome of the pregnancy.

6.6.2 Paternal exposure

Male subjects should refrain from fathering a child or donating sperm during the study and 1 month following the last dose.

Pregnancy of the subject's partners is not considered to be an adverse event. However, the outcome of all pregnancies (spontaneous miscarriage, elective termination, ectopic pregnancy, normal birth or congenital abnormality), should, if possible, be followed up and documented in the Pregnancy Report Form. Consent from the partner must be obtained before the Pregnancy Report Form is completed.

6.7 Medication Error

For the purposes of this clinical study a medication error is an unintended failure or mistake in the treatment process for an AstraZeneca study drug that either causes harm to the subject or has the potential to cause harm to the subject.

A medication error is not lack of efficacy of the drug, but rather a human or process related failure while the drug is in control of the study site staff or subject.

Medication error includes situations where an error.

- occurred
- was identified and intercepted before the subject received the drug
- did not occur, but circumstances were recognized that could have led to an error

Examples of events to be reported in clinical studies as medication errors:

- Drug name confusion
- Dispensing error e.g. medication prepared incorrectly, even if it was not actually given to the subject
- Drug not administered as indicated, for example, wrong route or wrong site of administration
- Drug not taken as indicated e.g. tablet dissolved in water when it should be taken as a solid tablet
- Drug not stored as instructed e.g. kept in the fridge when it should be at room temperature
- Wrong subject received the medication (excluding IVRS/IWRS errors)
- Wrong drug administered to subject (excluding IVRS/IWRS errors)

Examples of events that **do not** require reporting as medication errors in clinical studies:

- Errors related to or resulting from IVRS/IWRS - including those which lead to one of the above listed events that would otherwise have been a medication error
- Subject accidentally missed drug dose(s) e.g. forgot to take medication
- Accidental overdose (will be captured as an overdose)
- Subject failed to return unused medication or empty packaging
- Errors related to background and rescue medication, or standard of care medication in open label studies, even if an AZ product

Medication errors are not regarded as AEs but AEs may occur as a consequence of the medication error.

If an medication error occurs in the course of the study, then the Investigator or other site personnel informs the appropriate AstraZeneca representatives within 1 day i.e., immediately but **no later than 24 hours** of when he or she becomes aware of it.

The designated AstraZeneca representative works with the Investigator to ensure that all relevant information is completed within 1 or 5 calendar days if there is an SAE associated with the medication error (see Section 6.4) and within 30 days for all other medication errors.

7. INVESTIGATIONAL PRODUCT AND OTHER TREATMENTS

7.1 Identity of investigational product(s)

AZD9567 is a differentiated selective-Glucocorticoid-Receptor-Modulator. In the study the aim is to investigate the safety, efficacy and tolerability of AZD9567 compared to prednisolone in patients with active Rheumatoid Arthritis.

The drug substance is presented as a drug powder and formulated as a suspension for oral administration, using standard excipients. A placebo formulation, an oral suspension, using inactive standard excipients is included in the study. A comparator product, Prednisolone capsules and placebo for prednisolone capsules, will also be used.

Investigational product	Dosage form and strength	Manufacturer
AZD9567 Oral suspension	0.5 mg/ml - 10 mg/ml	AstraZeneca R&D Gothenburg
AZD9567 Oral suspension	Placebo	AstraZeneca R&D Gothenburg
OC Prednisolone capsules	5 mg	AstraZeneca R&D Gothenburg
OC Prednisolone capsules	Placebo	AstraZeneca R&D Gothenburg

7.2 Dose and treatment regimens

A total of 40 eligible patients will be randomly assigned 1:1 to the study treatment. This will be managed via IWRS. The dose of IP, AZD9567 40 mg and prednisolone 20 mg, will be

taken once daily (in the morning) for 14 days. Detailed instructions are provided in the Handling instructions each patient will be provided with in local language. The first dose of IMP will be taken at the clinic after the baseline assessments have been performed on Visit 2. Also at the end of treatment visit, Visit 5, the IMP should be taken at the site to allow for a pre dose blood sample to be drawn for PK analyses. As the IMP has different formulations, double dummy technique is applied. Each patient will therefore take both oral suspension and 4 capsules of prednisolone/placebo on a daily basis for 14 days. The oral suspensions of AZD9567 and placebo are not taste neutral. This information will be included in the Patient Informed Consent form. Opening aids for the IMP bottles will be supplied by AstraZeneca and will be described in the Handling instructions.

7.3 Labelling

Labels will be prepared in accordance with Good Manufacturing Practice (GMP) and local regulatory guidelines. The labels will fulfil GMP Annex 13 requirements for labelling. Label text will be translated into local language.

7.4 Storage

All study drugs should be kept in a secure place under appropriate storage conditions. Details of storage condition will be provided on the label of the IMP. The IMP storage area must be temperature monitored and the site will maintain documentation of the temperature monitoring. Handling instructions for the patients will be provided separately by AstraZeneca.

7.5 Compliance

The administration of all study drugs should be recorded in the appropriate sections of the Case Report Form.

7.6 Accountability

The study drug provided for this study will be used only as directed in the Clinical Study Protocol.

The study site staff will account for all study drugs dispensed to and returned from the subject.

The study drug should be destructed locally. Study site staff, if applicable, or the AZ monitor will account for all study drugs received at the site, unused study drugs and for appropriate destruction. Certificates of delivery and destruction should be signed.

7.7 Concomitant and other treatments

7.7.1 Other concomitant treatment

Pre-clinical *in vitro* data indicate that AZD9567 can inhibit drug transporters such as P-glycoprotein and breast cancer receptor protein. Therefore, digoxin should not be given

together with the IMP due to the risk for elevated plasma levels of digoxin. To avoid drug-drug interaction risks for statins, simvastatin, atorvastatin, rosuvastatin and fluvastatin dose administration should be separated in time such as the AZD9567 is taken in the morning and the statin in the evening.

AZD9567 is metabolised via CYP3A4 and hence moderate and strong inhibitors or inducers of CYP3A should not be administered during this study since that will affect the plasma concentration of AZD9567. Patients should not have taken any of these medications within 3 days of IMP intake (ref exclusion criteria 5). Guidance is provided in [Appendix E](#). However, the list in Appendix E is not a complete list, ie it should be treated with caution.

Guidance for avoiding QT-prolonging medications can also be found in a link provided in [Appendix E](#).

Other medication, which is considered necessary for the subject's safety and wellbeing, may be given at the discretion of the Investigator and recorded in the appropriate sections of the Case Report Form.

8. STATISTICAL ANALYSES BY ASTRAZENECA

8.1 Statistical considerations

The purpose of this section is to provide a brief outline of the statistical methods to be employed in this Phase IIa, Randomised Multi-Center, Double- Blind, comparator-Controlled Study of AZD9567 xx mg in patients with Rheumatoid Arthritis (RA) and prednisolone 20 mg. A more detailed description of all statistical matters as well as data derivations and data summaries will be included in separate statistical analysis plan (SAP) based on the current protocol and in accordance to the International Conference on Harmonization (ICH) E3 and E9 Guidelines.

All efficacy and safety variables will be summarized by treatment groups using descriptive statistics (n, mean, standard deviation [SD], median, minimum, and maximum for continuous data and absolute and relative frequencies for categorical data). Data will be summarized for baseline, endpoint and by visit (if applicable).

Descriptive statistics will be presented to assess the distribution of the baseline variables across treatment groups. Assessment of efficacy will be made using the decision framework (cf. 8.2) used to determine the necessary sample size. Formal statistical tests for differences between treatment groups will be applied for exploratory purposes only. Moreover

- All personnel involved with the analysis of the study will remain blinded until database lock and Clinical Study Protocol violators identified.
- Analyses will be performed by AstraZeneca or its representatives.

- Refer to Statistical Analysis Plan (SAP) for details.

8.2 Sample size estimate

This study, is a Phase IIa study, where the aim is to show that the efficacy of AZD9567 is equivalent to the efficacy of prednisolone 20 mg. The design is a two arm design, one arm receiving prednisolone 20 mg and the other receiving AZD9567.

The endpoint proposed is the change from baseline (CFBL) in DAS28 units for each patient. The main analysis will be based on the difference $X_T - X_P$, between X_T , the average change from base line of the chosen dose of AZD9567 and, X_P , the mean CFBL of prednisolone 20 mg. Therefore, this difference quantifies the treatment effect i.e. how much better AZD9567 is compared to prednisolone 20 mg in terms of average CFBL in DAS28 units.

The details of the sample size calculation are based on internal decision criteria as explained in [Frewer et al, 2016](#). In these calculations we use the reliability threshold of the DAS28 index known to be 0.6 ([Siemons et al, 2014](#)).

Using a sample size of 18 per arm, results in good decision criteria. In comparison with traditional hypothesis testing this corresponds to a test with significance level $\alpha=0.09$ and $\beta=0.10$.

The above results have been evaluated using simulations. Further details of the statistical methodology will be outlined in the SAP.

8.3 Definitions of analysis sets

8.3.1 Efficacy analysis set

The primary analysis population for efficacy will be analyzed using the intention to treat (ITT) population. This is in accordance to the ICH E9 guideline suggesting that the analysis of the primary endpoint should be analyzed according to the treatment to which patients were actually randomised. The ITT population will include all patients who were randomised and received at least one dose of study medication. Patients will be analyzed according to the treatment to which they were intended to be randomised to. ITT is sometimes referred to as Full Analysis Set.

Moreover, the primary analysis population for efficacy will also be analyzed using the Per Protocol (PP) population which includes all patients who were randomised, treated with study medication and did not have a major protocol deviation. Major protocol deviations leading to exclusion from the PP population will be finalized prior to un-blinding during the blind data review meeting. Full criteria for exclusion from the analysis set will be detailed in the Statistical Analysis Plan (SAP).

8.3.2 Safety analysis set

The Safety Population will include all patients who were randomised and received at least one dose of study medication. Patients will be analyzed according to the treatment which they actually received.

8.3.3 PK analysis set

The PK analysis set will include all subjects with at least one quantifiable AZD9567 concentration with a documented related dosing history.

8.3.4 Other analysis sets

Pharmacodynamic (PD) analysis set will include all subjects who received at least one dose of study treatment and have available pharmacodynamic data.

8.4 Outcome measures for analyses

The primary efficacy endpoint is the difference in change from baseline in DAS28, $X_T - X_p$, between, X_T , the average CFBL of the chosen dose of AZD9567 and, X_p , the mean CFBL of prednisolone 20 mg.

Secondary efficacy variables are the change from baseline in ACR and the percentage of patients with ACR20, 50 and 70.

8.5 Methods for statistical analyses

8.5.1 Analysis of the primary variable(s)

To show that the efficacy of AZD9567 is equivalent to the efficacy of p20 mg in terms of change from baseline in DAS28, we will use the difference in DAS28 units, $X_T - X_p$, between, X_T , the average CFBL of the chosen dose of AZD9567 and, X_p , the mean CFBL of prednisolone 20 mg. This difference will be calculated using a mixed model. It will be concluded that the data support better efficacy of AZD9567 whenever the observed difference is positive (larger than 0). Similarly, it will be concluded that the AZD9567 is less efficacious than prednisolone 20 mg if the difference is negative (less than -0.4). Formal statistical testing will be performed for exploratory purposes only.

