3. PRIMARY AND SECONDARY VARIABLES

3.1 Primary Variable

The difference in DAS28 units will be used to show that the efficacy of AZD9567 40 mg is equivalent to the efficacy of Prednisolone 20 mg at Day 15:

$$\text{Diff} = X_T - X_P$$

where X_T is the mean change from baseline in DAS28 of AZD9567 and X_P is the mean change from baseline in DAS28 of Prednisolone.

DAS28 scores will be derived at baseline and each post-baseline assessments using the following formula:

$$\begin{aligned} \text{DAS28 (CRP)} = & 0.56 * \sqrt{TJC28} + 0.28 * \sqrt{SJC28} + 0.014 * GH + 0.36 * \ln(CRP + 1) \\ & + 0.96 \end{aligned}$$

Where:

$TJC28$ = 28 joint count for tenderness (Section 3.1.1 [Tender Joint Counts](#)).

$SJC28$ = 28 joint count for swelling (Section 3.1.2 [Swollen Joint Counts](#)).

Global health (GH) = subject's global assessment on Visual Analogue Scale (VAS) of 100 mm (Section 3.1.3 [Global Health](#)).

$\ln(CRP)$ = natural logarithm of CRP (mg/L) (Section 3.1.4 [CRP](#)).

Refer to Section 4.4.1 Missing DAS28 (CRP) for handling of missing DAS28 (CRP) components.

The following supplementary variables will be used to calculate the primary variable DAS28:

3.1.1 Tender Joint Count 28

The following 28 joints (14 left, 14 right) will be evaluated for tenderness as obtained from the Joint Count Right or Left electronic case report form (eCRF):

- 2 each: Interphalangeal joints of the thumbs, wrist joints, elbow joints, shoulder joints, knee joints.
- 8 Proximal interphalangeal (PIP) joints of the fingers.
- 10 Metacarpophalangeal joints (MCP) joints.

The tender joint count represents the number of joints in which pain is reported after either manoeuvre.

$TJC28$ = Sum of tender joints with present status on the eCRF. Maximum $TJC28 = 28$.

Refer to Section 4.4.2 Missing tender or swollen joints for missing joint counts.

3.1.2 Swollen Joint Count 28

The same joints mentioned in Section 3.1.1 will be evaluated for swelling.

The swollen joint count represents the number of joints in which there is synovial fluid and or soft tissue swelling, but not if bony overgrowth is found.

SJC28 = Sum of swollen joints with present status on the eCRF. Maximum SJC28 = 28.

Refer to Section 4.4.2 Missing tender or swollen joints for missing joint counts.

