4.3.1 Primary efficacy statistical model

Formal statistical testing will be performed for exploratory purposes only.

The default significant level will be two-sided 5%, CIs will be 95% and all tests will be two-sided, unless otherwise specified in the description of the analyses. Two-sided p -value ≤ 0.05 will be considered statistically significant.

Confidence intervals (CIs) for the true difference in means, $\mu_{\text{AZD9567}} - \mu_{\text{Prednisolone}}$, will be calculated using the estimated treatment effect and the mean square error.

A MMRM is to be used to examine the primary efficacy variable, using the PROC MIXED procedure in SAS.

The MMRM model will include the baseline DAS28 score as a covariate.

The MMRM model will include categorical fixed effects of treatment, visit, treatment-by-visit interaction and country:

- Change from baseline (at Day 15) = Treatment group baseline DAS28 score Treatment group*visit
- Treatment group = AZD9567 or Prednisolone.
- Visit = Day 8 and Day 15.
- Country = Netherlands or Sweden
- Change from baseline (at Day 15) = Change in DAS28 from baseline at Day 15.

An unstructured matrix for the within-subject error variance covariance will be used. The denominator degrees of freedom will be calculated according to the Kenward-Roger method.

In case of non-convergence of the preferred model or memory space issues the following models will be explored in the order given:

1. Country may be removed from the model.
2. The second backup model is the same as the preferred model but the Kenward-Roger method will be replaced by Satterthwaite approximation.

The least squares mean (LSM) change from baseline in DAS28 score and corresponding standard error (SE) and 95% confidence interval (CI) by treatment group at Day 8 and Day 15 will be provided in a table. The least squares mean difference (LSMD) between the two

treatment groups at Day 8 and Day 15 and corresponding 95% CI and two-sided p-value will also be presented in the table.

A figure will be provided displaying the LSM change from baseline by treatment group and visit, along with the 95% CI.

The FAS and PP analysis sets will be used for primary efficacy with FAS analysis set as primary interest.

Results for the PP analysis will be tabulated and displayed graphically in the same manner as the primary analysis.

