6. CHANGES OF ANALYSIS FROM PROTOCOL

Table 2 Summary of changes from protocol

Reference	Protocol	Change	Justification
SAP Section 1.1.4	Section 2.4.	
The following exploratory endpoints will be included:
 
• European League Against Rheumatism (EULAR) response criteria.• DAS28 remission.• Clinically important change.• Low disease activity.	Additional endpoints considered important for efficacy interpretation by study team.
SAP Section 1.3	Section 8.2.	
Comparison to traditional hypothesis testing has been removed and replaced with a statement that the study is “not sufficiently powered to support hypothesis testing”.
 
The sample size of “n=18” per arm has been updated to “n=10” per arm.
	
Power of the study expected to be lower than that stated in the protocol, given the sample size and expected effect size. Wording updated to remove power calculation.
 
Update to n reflects agreement to close recruitment early. Hence a reduced n per arm was agreed.

SAP Section 4.2.1	Section 8.5.1	Concluded that the difference in mean CFB in DAS28 of AZD9567 - mean CFB in DAS28 of Prednisolone will show a better efficacy if the observed difference negative (less than 0) instead of positive (larger than 0).	Lower DAS28 score is better.

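### The primary conclusion rests on the point estimate alone, no result is defined as the equivalence the trial sets out to show, and the -0.4 cut-off was left behind when the SAP reversed the sign

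*Protocol*

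**What the plan says.** **Aim.** Protocol 8.2 describes a study "where the aim is to show that the efficacy of AZD9567 is equivalent to the efficacy of prednisolone 20 mg". SAP 3.1 keeps that aim: "The difference in DAS28 units will be used to show that the efficacy of AZD9567 40 mg is equivalent".

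**Rule.** Protocol 8.5.1 gives two conclusions, both read from the observed difference (AZD9567 minus prednisolone in mean change from baseline in DAS28). The first is "It will be concluded that the data support better efficacy of AZD9567 whenever the observed difference is positive (larger than 0"). The second is "it will be concluded that the AZD9567 is less efficacious than prednisolone 20 mg if the difference is negative (less than -0.4"). Nothing is said about values between -0.4 and 0.

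**SAP change.** Section 6, Table 2 notes that a lower DAS28 is better, so the difference "will show a better efficacy if the observed difference negative (less than 0) instead of positive (larger than 0"). Table 2 does not mention the -0.4 cut-off. It points to SAP 4.2.1, which contains no decision rule.

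**Sizing.** Protocol 8.2 states: "In these calculations we use the reliability threshold of the DAS28 index known to be 0.6". It says that for 18 per arm "this corresponds to a test with significance level $\alpha=0.09$ and $\beta=0.10". SAP 1.3 replaces 18 with 10 per group and says this is too few to support hypothesis testing.

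**Outputs.** SAP 4.3.1 plans the LS mean difference with 95% CI and p-value at Days 8 and 15, in FAS (primary) and PP. SAP 4.7 adds an ANCOVA with its own 95% CI. Section 4.3.1 states "Two-sided p -value ≤ 0.05 will be considered statistically significant", having opened by calling formal testing exploratory. No margin is given against which to read the intervals.

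**The concern.** There are three linked gaps.

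1. 'Better' depends only on the sign of the estimate. The standard error plays no part, so a trivial or chance difference earns the label.
2. The stated aim has no success criterion. The rule labels 'better' and 'less efficacious', leaves the range between them unlabelled, and never says what result would show equivalence.
3. The two cut-offs now point in incompatible directions. Table 2 moved one and was silent on the other.

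What is at stake is the headline statement of the study report. It could claim better efficacy without support, or carry two contradictory labels for the same number.

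**Working it through.** **1. The plan's own figure.** Protocol 8.2 gives 18 per arm, alpha 0.09 and beta 0.10, but no SD and no sidedness. Solving SD = delta / [(z_alpha + z_beta) x sqrt(2/n)], where sqrt(2/18) = 0.333:
- delta 0.6, one-sided: 0.6 / [(1.341 + 1.282) x 0.333] = 0.686
- delta 0.6, two-sided: 0.6 / [(1.695 + 1.282) x 0.333] = 0.605
- delta 0.4: 0.458 (one-sided) or 0.403 (two-sided)

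So 18 per arm can be neither confirmed nor refuted. In the one-sided 0.6 version, with the null at -0.6 (positive = benefit), SE = 0.686 x 0.333 = 0.229. The decision cut-off would be -0.6 + 1.341 x 0.229 = -0.29, which is neither of the printed values, 0 and -0.4.

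**2. Identical drugs.** The estimator is symmetric about 0, so P('better') = 0.50 whatever n and SD. Simulation gave 0.499 at n = 10 and 0.500 at n = 18. Reversing the sign does not change this.

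**3. Behaviour at 10 per arm.** SE = SD x sqrt(2/10). With the sign aligned so that both cut-offs run the same way and AZD9567 truly 0.6 worse:
- P('better') = Phi(-0.6/SE)
- P('less efficacious') = Phi((0.6 - 0.4)/SE)

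The 95% CI half-width is 2.12 x SE, using t on 16 df (20 patients less intercept, treatment, baseline and country). The last column is simulated: the chance, with identical drugs, that a 90% CI lies within an illustrative +/-0.6. The SDs are assumptions. The first two are those implied in step 1, and the rest are a wider range.

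| SD | SE | 'Better' if 0.6 worse | 'Less efficacious' if 0.6 worse | 95% half-width | 90% CI within +/-0.6, identical drugs |
|---|---|---|---|---|---|
| 0.605 | 0.271 | 1.3% | 77% | 0.57 | 37% |
| 0.686 | 0.307 | 2.5% | 74% | 0.65 | 21% |
| 0.8 | 0.358 | 4.7% | 71% | 0.76 | 8% |
| 1.0 | 0.447 | 9.0% | 67% | 0.95 | 1% |
| 1.34 | 0.599 | 15.8% | 63% | 1.27 | <0.1% |

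If the planned 95% CI had to lie within +/-0.6 instead, the chance would be about 7% at SD 0.686 and 0.1% at SD 1.0.

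**4. The unlabelled zone.** With identical drugs and aligned signs, P('less efficacious') = Phi(-0.4/SE), which is 7% at SD 0.605 and 25% at SD 1.34. The zone between the cut-offs takes the remainder, 50% - 7% = 43% down to 50% - 25% = 25%.

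**5. The sign clash.** Take a difference of -0.5. It is below 0, so Table 2 says 'better'. It is also below -0.4, so protocol 8.5.1, unchanged on this point, says 'less efficacious'. By symmetry with step 3, a drug truly better by 0.6 would fall in this doubly labelled region in 63% to 77% of trials. A positive difference would carry no label.

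**The case against.** The strongest defence is context. This is a Phase 2a study, formal testing is declared exploratory, the rule speaks only of what the data support, the SAP discloses low power, and confidence intervals will be reported beside the estimate. Protocol 8.1 also refers efficacy assessment to a decision framework, and 8.2 gives operating characteristics for it. That lowers the severity. It does not fill the gap: 8.2 prints no criteria, the SAP prints none, and Table 2 removes the alpha and beta comparison. Nor is the point-estimate rule itself labelled exploratory.

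A reader might infer more than the documents support:
- *That equivalence could never be concluded.* The zone between the cut-offs might be meant as 'similar'. Neither document says so, and it would still be a one-sided range judged on the point estimate. The accurate criticism is that the zone is undefined.
- *That a two-sided test is the only inference planned.* It is not: 95% CIs are planned for both MMRM and ANCOVA.
- *That a non-significant p-value will be presented as equivalence.* Nothing in the text says this.
- *That 0.6 is the equivalence margin.* The documents call it a reliability threshold and use it only in sizing.
- *That the rule has no power to detect a worse drug.* With signs aligned, it flags a 0.6 deficit in 63% to 77% of trials at 10 per arm.
- *That reversing the sign in the SAP is an error.* It is a declared correction with a valid reason. The fault is that it stopped at one of the two cut-offs.

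**Conclusion.** The point stands and should be fixed. 'Better efficacy' is concluded from the sign of an estimate, the stated aim of equivalence has no defining result, and the -0.4 cut-off conflicts with the revised direction.

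The 50% figure needs only a symmetric estimator. The figures of 1% to 16% for a drug 0.6 worse being called 'better', and of about 0.6 to 1.3 for the half-width, rest on an assumed SD of about 0.6 to 1.34, a normal approximation for the rule and 10 evaluable patients per arm. The equivalence probabilities, at most about 37% over the SDs tabulated, also depend on the illustrative +/-0.6 margin. Even on the SDs most favourable to the plan, showing equivalence at this sample size is unlikely.

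**What to change.** Before unblinding, in SAP Table 2 and protocol 8.5.1, and stated also in SAP 4.2.1 where Table 2 says the rule sits:

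1. Replace the point-estimate rule with one on the Day 15 MMRM difference and its CI, in FAS with PP supportive. Conclude 'better' only if the 95% CI excludes 0 in AZD9567's favour. Otherwise report the estimate and CI as inconclusive, unless an equivalence criterion under item 2 is met.
2. Choose one of two courses on equivalence. Either state a margin with its justification and the CI level, and require the CI to lie within the margin (0.6 is a candidate, but the choice is the sponsor's to defend). Or reword SAP 3.1 so that the aim is to estimate the difference. The second course fits the SAP's own statement about 10 per group.
3. Restate the -0.4 cut-off with the sign that matches Table 2, or remove it.

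The cost is wording in the SAP and the matching protocol text. The model and 95% CIs are already planned, and a 90% CI, if chosen, comes from the same fit. The real downside is that the likely stated conclusion becomes less favourable: 'inconclusive'.
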